Appendix C. Code Fragments

95% Confidence Interval by Clopper Pearson Method

and 0 is flagged for censored observation.

proc freq data= <data>;</data>
tables <variable>/ binomial(exact) ;</variable>
run;
Kaplan Meier Method
proc lifetest data= <data> <conftype=linear and="" brookmeyer="" crowley="" for="" method=""> <conftype=loglog and="" for="" kalbfleisch="" method="" prentice="">;</conftype=loglog></conftype=linear></data>
time T * Status(0);
run;
where
T is time to event;
Status is censoring variable:

Date: 24 March 2023 Page 49 of 53

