9.2 Sample Size Determination

The sample size in the dose exploration phase is based on practical consideration and is consistent with conventional oncology studies with the objective to estimate the MTD. With 3 subjects in a dose level, there is a 27% to 70% probability of observing at least 1 DLT if the true DLT rate is 10% to 33% and with 4 subjects in a dose level, there is 34% to 80% probability. With 6 subjects in a dose level, there is a 47% to 91% probability of observing at least 1 DLT if the true DLT rate is 10% to 33% and with 10 subjects in a dose level, there is a 65% to 98% probability.

In the dose expansion phase, a subject number of 40 will provide an 87% probability of observing at least 1 adverse event with 5% incidence rate. With the 40 subjects and 20% overall response rate, the expected 95% CI would be 9% to 36%.

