9.4.2.2 Efficacy Analyses

Endpoint	Statistical Analysis Methods
Primary	Not applicable
Secondary	Listings of secondary efficacy endpoints will be produced for all subjects. The proportion of subjects with an objective response (OR) (per RECIST 1.1 guidelines [Sections 11.8 and 11.9]) and 95% CI will be tabulated by planned dose level. Disease control rate and 95% CI will be tabulated by planned dose level. For all subjects treated at the MTD and/or RP2D, Kaplan-Meier methods will be used to estimate the time to event curve, median time to event and percentiles with 95% CI for 1) duration of response (DOR), 2) progression-free survival (PFS), 3) OS. For all subjects treated at the MTD and/or RP2D, Kaplan-Meier methods will be used to estimate landmarks for time to event events (eg, PFS and OS at 6 and 12 months) with 95% CI.
Exploratory	Will be described in the statistical analysis plan finalized before database lock

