For the interim analysis, data will be subject to ongoing checks for integrity, completeness and accuracy with the expectation that outstanding data issues for selected CRF pages as deemed critical by the study team are resolved ahead of the snapshot to the extent possible. All available data up to and including the data cut-off date will be included in the analysis based on an "as-is" snapshot of the database with targeted data cleaning without data locking.

The Target Value (TV) is set to demonstrate a 18% increase in ORR (i.e., TV = 30%) over the benchmark 12% ORR. For Part 2, at final analysis:

 NoGo criteria will be met if the probability that the true ORR exceeds the pre-specified TV of 30% is less than 5% (i.e., NoGo: P[ORR > TV] < 5%).

Given the existing observed data during the continuous monitoring stage, the Bayesian predictive probability is obtained by calculating the probability of reaching a NoGo decision should the treatment group be enrolled and evaluated to the maximum planned final sample size of 40 in each group in Part 2. Further enrollment to the respective group in Part 2 may be terminated if futility criteria are met. Notice the NoGo criteria is for interim futility analysis purpose only.

 Futility is met if it is predicted that there is a high probability of reaching a NoGo decision upon full enrollment of 40 subjects in the respective group in Part 2

Date: 24 March 2023 Page 30 of 53

given the existing observed data (ie, predictive probability of a NoGo decision > 95%).

The decision matrix for continuous monitoring of ORR is provided in Figure 7-1 assuming a prior distribution of Beta (1, 1). For example, given TV of 30%, 3 or fewer observed responders after 30 subjects have reached the data cutoff criteria would trigger stopping enrollment claiming futility due to a high probability of reaching a NoGo decision upon full enrollment to 40 subjects in the respective group, given the existing observed data in that group.

Figure 7-1. Decision Matrix for Continuous Monitoring of ORR

Operating characteristics of this continuous monitoring method are presented in Table 7-3 and are based on 100 000 simulations using the prespecified TV value, and NoGo and Futility definitions.

A false NoGo is defined as observing either futility criteria during the continuous monitoring stage or NoGo criteria at final analysis when the true ORR is greater than or equal to the TV (ie, False NoGo: P[Futility or NoGo Decision | True ORR ≥ TV]).

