9.1 General Considerations

Analyses will be split by study part and group (for part 2 only) unless otherwise specified

Descriptive statistics will be provided for selected demographics, exposure, safety, PK, efficacy data. Descriptive statistics on continuous data will include means, medians, standard deviations and ranges, while categorical data will be summarized using frequency counts and percentages. Graphical summaries of the data may also be presented. Confidence intervals (CI) for proportions will be estimated using an exact method proposed by Clopper-Pearson (Clopper and Pearson, 1934). Kaplan-Meier methods will be used to estimate the median and percentiles for time to event endpoints with CI calculated using the Brookmeyer and Crowley (Brookmeyer and Crowley, 1982) method. Kaplan-Meier methods will be used to estimate landmarks for time to event endpoints (e.g., 1-year overall survival [OS]) with the Greenwood formula (Kalbfleisch and Prentice, 1980) used to estimate the standard error used in CI calculation.

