Duration of response (DOR) per RECIST 1.1	The distribution of DOR, including the median and percentiles will be summarized using the Kaplan-Meier (KM) method with CI calculated using the Brookmeyer and Crowley (Brookmeyer and Crowley, 1982) method. Landmarks at the selected time points (e.g. 3, 6, 9 and 12 months) will be reported along with	Local data: RECIST 1.1 Evaluable by Investigator Assessment Analysis Set; Central data:

Product: Tarlatamab (AMG 757) Protocol Number: 20200040 Date: 24 March 2023

Page 36 of 53

Endpoint	Statistical Analysis	Analysis Set
	95% CI using the Greenwood formula	RECIST 1.1
	(Kalbfleisch and Prentice, 1980) to estimate the	Evaluable by
	standard error in CI calculation.	Central
		Reviewer
		Analysis Set
Radiographic	The distribution of rPFS, including the median	Interim: Interim
progression-free	and percentiles will be summarized using the	Efficacy
survival (rPFS) per	Kaplan-Meier (KM) method with CI calculated	Analysis Set
RECIST 1.1 with	using the Brookmeyer and Crowley	Primary/Final:
PCWG3	(Brookmeyer and Crowley, 1982) method.	Safety
modifications	rPFS rate at the selected time points (e.g. 3, 6,	Analysis Set
	9 and 12 months) will be reported along with	7
	95% CI using the Greenwood formula	
	(Kalbfleisch and Prentice, 1980) to estimate the	
	standard error in CI calculation.	
Overall survival	The distribution of OS, including the median	Interim: Interim
(OS)	and percentiles will be summarized using the	Efficacy
	Kaplan-Meier (KM) method with CI calculated	Analysis Set
	using the Brookmeyer and Crowley	Primary/Final:
	(Brookmeyer and Crowley, 1982) method. OS	Safety
	rate at the selected time points (e.g. 3, 6, 9 and	Analysis Set
	12 months) will be reported along with 95% Cl	7 triary 515 CCt
	using the Greenwood formula (Kalbfleisch and	
	Prentice, 1980) to estimate the standard error	
	in CI calculation.	
Disease c ontrol	The proportion of subjects with disease control	Local data:
rate (DCR) per	(i.e. a BOR of CR, PR or SD) with	RECIST 1.1
RECIST 1.1	corresponding exact 95% CI will be calculated	Evaluable by
	using the Clopper-Pearson (Clopper and	Investigator
	Pearson, 1934) method.	Assessment
		Analysis Set;
		Central data:

Product: Tarlatamab (AMG 757) Protocol Number: 20200040 Date: 24 March 2023

Page 37 of 53

Endpoint	Statistical Analysis	Analysis Set
		RECIST 1.1
		Evaluable by
		Central
		Reviewer
		Analysis Set

[figure not shown]

Table 9-2. Exploratory Efficacy Endpoint Summary Table

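### The linear transform set in SAP Appendix C makes the nominal 95% interval for median duration of response cover about 87% to 90% on average at the likely responder numbers

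*SAP*

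**What the plan says.** SAP 9.1 says Kaplan-Meier methods will be used to "estimate the median and percentiles for time to event endpoints with CI calculated using the Brookmeyer and Crowley" method. Table 9-1 repeats this for DOR: "The distribution of DOR, including the median and percentiles will be summarized using the Kaplan-Meier (KM) method". Protocol 9.4.2.1 names the same method, and Protocol 9.4.2.2 sets the level: "median time to event and percentiles with 95% CI". None of these passages names a transform of the survival scale.

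Appendix C of the SAP does. Its SAS fragment reads "proc lifetest data= <data> <conftype=linear", labelled as the option for Brookmeyer and Crowley. It then gives "<conftype=loglog", labelled as the option for Kalbfleisch and Prentice, the reference that 9.1 and Table 9-1 cite for landmark rates. Medians and percentiles therefore get linear limits, and landmark rates get log-log limits. The SAP's change log records that these options were added deliberately.

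**The concern.** A Brookmeyer-Crowley interval collects the times at which the Kaplan-Meier curve is statistically compatible with 50%. On the linear scale it relies on a normal approximation to S(t) itself. That is poor when the curve rests on about ten subjects, and it drops event times that should stay in the interval.

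DOR is the endpoint exposed to this. SAP 5.3 defines it only for subjects with an objective response, and SAP 9.1 states: "Analyses will be split by study part and group (for part 2 only) unless otherwise specified". There is no comparator and no hypothesis test, so the interval is the main statement of uncertainty about durability. If a nominal 95% interval misses the true median 10% to 13% of the time on average, that statement is too favourable.

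**Working it through.** **Inputs from the documents.** The largest group is 40: SAP 7.1 gives a "maximum planned final sample size of 40 in each group in Part 2". The current protocol also has 40 subjects in Part 2, so the count per analysed group is the same under both documents. The response rates are 20% (Protocol 9.2), the 30% target and the 12% benchmark (SAP 7.1). These imply 40 × 0.20 = 8, 40 × 0.30 = 12 and 40 × 0.12 ≈ 5 responders.

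**Plan's own figure.** Protocol 9.2 says: "With the 40 subjects and 20% overall response rate, the expected 95% CI would be 9% to 36" percent. Clopper-Pearson limits for 8/40 are 9.05% and 35.65%, which agrees. The documents give no coverage figure for a median.

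**Exact coverage without censoring.** After k of n events, S = (n−k)/n and SE = √(S(1−S)/n).
- Linear keeps k if |S − 0.5| ≤ 1.96·SE.
- Log-log keeps k if |log(−log S) − log(log 2)| ≤ 1.96·SE / |S·log S|.

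If k = a,…,b are kept, the interval runs from event time a to event time b+1. Coverage is then P(a ≤ Bin(n, ½) ≤ b).

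Example, n = 12. At k = 3, S = 0.75 and SE = 0.125. Linear compares 0.25 with 1.96 × 0.125 = 0.245 and drops the time. The log-log limits at the same time are about 41% to 91%, which include 50%. Linear keeps k = 4 to 8, so coverage is 3498/4096 = 85.4%. Log-log keeps k = 2 to 9, so coverage is 1 − 92/4096 = 97.8%.

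| Responders | Linear | Log-log |
|---|---|---|
| 3 | 75.0% | 75.0% |
| 4 | 87.5% | 87.5% |
| 5 | 93.8% | 93.8% |
| 6 | 78.1% | 96.9% |
| 8 | 93.0% | 96.1% |
| 9 | 82.0% | 97.9% |
| 10 | 89.1% | 94.4% |
| 12 | 85.4% | 97.8% |
| 40 | 91.9% | 94.0% |

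**Average over the responder count.** The number of responders is itself random, so weight coverage C(n) by Bin(40, ORR): Σ P(n)·C(n) / P(N ≥ 3), summed over n ≥ 3.

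| ORR | Linear | Log-log |
|---|---|---|
| 12% | 85.3% | 89.9% |
| 20% | 87.4% | 94.8% |
| 30% | 89.7% | 95.7% |

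The starting point matters a little. Beginning at 5 responders raises the log-log figure at 20% ORR to 95.6%.

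**With censoring (assumed).** The documents give no censoring rate or DOR distribution. I simulated exponential durations with uniform censoring between 0.5 and 3 medians (about 34% censored, 100,000 runs per count). An open upper limit counted as covering.

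| Responders | Linear | Log-log |
|---|---|---|
| 8 | 90.6% | 96.0% |
| 9 | 84.7% | 96.6% |
| 10 | 89.2% | 95.3% |
| 11 | 91.5% | 96.1% |
| 12 | 88.2% | 96.4% |

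The simple means over these five counts are 88.8% and 96.1%. A second model used 12 or 24 months of accrual plus 6 months of follow-up and true medians of 4, 6 or 9 months. Averaged over the responder count, it gave 87.3% to 88.7% (linear) against 94.0% to 94.9% (log-log) at 20% ORR. At 30% ORR it gave 89.7% to 90.8% against 95.5% to 95.8%.

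**The case against.** The strongest reply is that the plan contains no error. Brookmeyer-Crowley is the named method, the linear form is a recognised way to compute it, and each transform is prespecified under its own reference. That is fair as far as it goes: the SAP does not contradict the protocol, and using two transforms for two quantities is not in itself a conflict. It does not answer the coverage problem, because the rule followed exactly still gives a 95% label to an interval that falls short of it.

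Several stronger readings are tempting and should be resisted.
- **That rPFS and OS medians are equally affected.** They use the Safety Analysis Set at the primary and final analyses, about 40 subjects per group. There linear gives 91.9% against 94.0% uncensored, and about 94% against 95% with the assumed censoring.
- **That the interval always misses more than twice as often as stated.** On average it does so at 20% to 30% ORR. But with exactly 8 uncensored responders the miss rate is 7.0%, or 1.4 times nominal. Coverage jumps with n, so 87% to 90% is an average and not a constant.
- **That log-log gives the correct width.** It over-covers at 9 and 12 responders (97.9% and 97.8%) and is identical to linear at 3 to 5 responders without censoring.
- **That a trial decision is at risk.** Futility rests on the response rate and expansion stopping on grade 4 or higher treatment-related events. Neither reads a DOR limit.

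It also stands that either interval will often look wide. With the assumed censoring the upper limit cannot be estimated in about 40% to 48% of linear intervals at 8 to 12 responders, and in about 45% to 56% of log-log intervals.

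**Conclusion.** The concern holds for median DOR. Under Appendix C, the nominal 95% interval covers on average about 87% at a 20% response rate and 90% at 30% without censoring, against about 95% and 96% on the log-log scale. The assumed censoring patterns leave this essentially unchanged. The uncensored figures are exact. The censored ones depend on assumed distributions, accrual and follow-up that the documents do not supply. The results also take 40 evaluable subjects per group; a smaller RECIST-evaluable set would mean fewer responders.

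The consequence is a secondary, descriptive result reported with too much precision. It is worth correcting before analysis because the correction is simple, but no primary endpoint or stopping rule depends on it.

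**What to change.** In SAP Appendix C, use the log-log option for medians and percentiles as well as for landmark rates. In SAP 9.1 and Table 9-1, add that Brookmeyer-Crowley intervals are computed on the log-log scale. The method is still the same inversion on a transformed scale, so the protocol wording stands and no protocol amendment is needed. It also gives the median and the landmark rates of one curve limits from the same transform.

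The cost is one program option and one sentence in each place. Intervals will be somewhat wider, the upper limit will more often be non-estimable, and some responder counts will be slightly over-covered. At 5 or fewer responders there is no gain: without censoring the two intervals coincide and coverage stays below nominal. At the 12% benchmark rate the log-log average is therefore still only about 90%.

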Appendix D. BOR per RECIST 1.1

BOR by investigator will be derived based on the timepoint response collected in the RECIST 1.1 CRF. BOR by central review will be derived from timepoint response shared by the central imaging vendor. At each time point, BOR will be derived based upon the evaluated timepoints up to and including the current MRI/CT assessment. The following rules will apply to BOR:

- CR is better than PR is better than SD is better than PD is better than NE
- For a BOR of SD, a duration of ≥ 49 days since the cycle 1 day 1 is required
- For a BOR of CR or PR confirmation is required. PR can be confirmed by a PR or CR. The confirmation assessment must be in a consecutive assessment ≥ 28 days after the initially observed assessment of CR or PR except the following cases:
 - An unlimited number of intermittent assessments of NE or CR <28 days can
 occur between the initial response and the confirmation of CR. For example,
 BL, CR, NE, NE, NE, CR the CR at post-baseline 1 is confirmed at postbaseline 5. SD is not allowed between CR and subsequent confirmation CR.
 - An unlimited number of intermittent assessments of NE, SD, PR or CR <28
 days can occur between the initial response and the confirmation of PR. For
 example, BL, PR, SD, SD, SD, PR the PR at post-baseline 1 is confirmed at
 post-baseline 5.

Table 14-3 provides the BOR determination per RECIST 1.1 where confirmation of response (CR/PR) is required. Table 14-4 outlines the steps to derive Confirmed_BOR (step 1) given timepoint assessments.

At interim futility analyses, due to lack of sufficient follow-up time for confirmation scan, study team may choose to report both confirmed responders and unconfirmed responders (subjects had an initial PR or CR and still has potential for future confirmative scans). Interim_BOR is defined to include unconfirmed responders in addition to those who achieve Confirmed_BOR. Table 14-4 step 2 provides details to derive the unconfirmed responders.

Table 14-3. BOR per RECIST 1.1 where Confirmation of CR/PR is Required

Criterio n	T1 .	days after	Timepoint T2 Response	T2 ≥ 49 days after	T2 ≥ 28 days after T1?	BOR_temp
	Response		response	C1D1?	uitoi i i i	

Date: 24 March 2023 Page 50 of 53

	1					
C1	CR	Yes	CR	-	Yes	CR
C2			CR	-	No	SD
C3			PR, SD	-	-	Query data*
C4			PD	-	-	SD
C5			NE, No furth	ner evaluat	ions	SD
C6		No	CR	-	Yes	CR
C7			CR	Yes	No	SD
C8			CR	No	No	NE
C9			PR, SD	-	-	Query data*
C10			PD	-	-	PD
C11			NE, No furth	ner evaluat	ions	NE
C12	PR	Yes	CR, PR	-	Yes	PR
C13			CR, PR	-	No	SD
C14			SD	-	-	SD
C15			PD	-	-	SD
C16			NE, No furth	ner evaluat	ions	SD
C17		No	CR, PR	-	Yes	PR
C18			CR, PR	Yes	No	SD
C19			CR, PR	No	No	NE
C20			SD	Yes	-	SD
C21			SD	No		NE
C22			PD	-	-	PD
C23			NE, No furth	ner evaluat	ions	NE
C24	SD	Yes	CR, PR, SD evaluation	, PD, NE, ı	no more	SD
C25		No	CR, PR, SD	Yes	-	SD
C26			CR, PR, SD	No		NE
C27			PD	-		PD
C28			NE, No furth	ner evaluat	ions	NE
C29	PD		-			PD
C30	NE	-	NE, No furth	ner evaluat	ions	NE
C31		-	CR, PR, SD	Yes	-	SD
C32		-	CR, PR, SD	No	-	NE
C33		-	PD	_	-	PD
~ -						

CR = complete response, PR = partial response, SD = stable disease, PD = progressive disease, NE = not evaluable.

*If a CR is truly met at first time point, then any disease seen at a subsequent time point, even disease meeting PR criteria relative to baseline, makes the disease PD at that point (since disease must have reappeared after CR). Best response would depend on whether minimum duration for SD was met. However, sometimes 'CR' may be claimed when subsequent scans suggest small lesions were likely still present and in fact the patient had PR, not CR at the first time point. Under these circumstances, the original CR should be changed to PR. A CR may also be followed by a PR when the target lesion assessment

Product: Tarlatamab (AMG 757)
Protocol Number: 20200040
Date: 24 March 2023
Page 51 of 53

is CR and the non-target lesion assessment is NE. In both of these situations, the best response is PR.

Table 14-4. BOR Derivation Step

Step 1. Derive Confirmed_BOR at each visit

Derive Confirmed BOR at each visit:

- At Visit 1: Use the Visit 1 scan result and refer to Table 14-3 to derive Confirmed BOR.
- ii) At Visit 2 onward:
 - (a) If current visit is CR: Find last scan that is not NE and at least 28 days before current visit. If current visit is PR: Find last scan that is not NE or SD and at least 28 days before current visit. Derive BOR temp as below:

Last scan	Current	BOR_temp
CR	CR	CR
PR	CR	PR
PR	PR	PR

- (b) If none of above fits, find last scan reference Table 14-3 to derive BOR_temp.
- iii) Current visit Confirmed_BOR = best of (BOR_temp, last visit confirmed_BOR). Use rule CR > PR > SD > PD > NE

Step 2. Derive Interim BOR at last visit prior to DCO

Step 2. Derive into	erini_BOK at last visit prior to DCO	
For subjects who discontinue	For subjects with potential for more assessment	
tumor assessment (i.e. had PD,	(i.e. no PD, next therapy, or end of study),	
next therapy, or end of study):	unconfirmed PR/CR can be considered	
	responders.	
Assign Interim_BOR =	If any scan is CR and haven't got the	
Confirmed_BOR	opportunity to receive next scan, then	
	Interim_BOR = CR.	
	If any scan is PR and haven't got the	
	opportunity to receive next scan, then	
	Interim_BOR = PR.	
	Else, Interim_BOR = Confirmed_BOR at the	
	latest scan.	

Date: 24 March 2023 Page 52 of 53

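### SAP Appendix D derives PR, SD, CR as SD but PR, SD, PR as PR, although its own text lets a CR confirm an earlier PR across SD

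*SAP*

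**What the plan says.** The text of SAP Appendix D sets the rule for confirmation. A CR or PR needs a consecutive confirming scan at least 28 days later, with two listed exceptions.

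- For a partial response, "PR can be confirmed by a PR or CR", and the scans allowed in between are "An unlimited number of intermittent assessments of NE, SD, PR or CR <28" days. The worked example is PR, SD, SD, SD, PR, which counts as a confirmed PR.
- For a complete response, NE scans may intervene, but "SD is not allowed between CR and subsequent confirmation CR".

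Table 14-4 step 1 turns this into a procedure with one look-back for each type of current scan:

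- The complete-response branch reads "If current visit is CR: Find last scan that is not NE and at least 28 days before current visit", so it passes over NE but stops at SD.
- The partial-response branch reads "If current visit is PR: Find last scan that is not NE or SD and at least 28 days before current visit", so it passes over both.

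The pairs that then give a response are CR/CR (CR), PR/CR (PR) and PR/PR (PR). Otherwise the instruction is "If none of above fits, find last scan reference" Table 14-3. Step iii carries the result forward as "Current visit Confirmed_BOR = best of (BOR_temp, last visit confirmed_BOR").

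The protocol is stricter. Table 1-3 footnote d and Section 8.2.2.1 ask for confirmation at a repeat consecutive assessment at least 4 weeks later, and the confirmation table in Appendix 8 maps PR followed by SD to SD. SAP Section 10, on changes from protocol-specified analyses, mentions only the analysis sets for interim efficacy.

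**The concern.** The CR look-back does two jobs. When the question is whether a CR is confirmed by another CR, stopping at an SD is right, because the text bars SD between the two. When the same CR could confirm an earlier PR, stopping at an SD conflicts with the text, which allows SD there. The table makes no distinction, so the PR is never reached.

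As a result, the text and the table give different answers for the same subject, and the table's answers are out of order. A subject whose last scan is PR is a responder, while a subject with the same history and a last scan of CR is not. Appendix D itself ranks CR above PR. ORR and DOR are secondary endpoints and depend on this derivation, so an affected subject leaves both the ORR numerator and the set of responders for DOR. Two programmers, one following the text and one the table, would disagree.

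**Working it through.** **Inputs.** Tables 14-3 and 14-4 and the Appendix D text (SAP). Scans every 8 weeks, with a 7-day window either side counted from first dose (protocol Table 1-3), so scheduled scans are at least 56 − 7 − 7 = 42 days apart. A BOR of SD needs at least 49 days from cycle 1 day 1 (SAP Appendix D). Expansion size 40 (protocol Section 9.2).

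**The SAP's own examples first.** Applying step 1 literally at 8-week spacing:

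- PR, SD, SD, SD, PR: the last PR skips the three SDs and finds the first PR, so PR/PR gives PR, as stated.
- CR, NE, NE, NE, CR: the last CR skips the NEs and finds the first CR, so CR/CR gives CR, as stated.

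**The two sequences side by side** (days 56, 112, 168):

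| Visit | PR, SD, **CR** | PR, SD, **PR** |
|---|---|---|
| 1 | PR, nothing further: row C16, SD | same, SD |
| 2 | PR then SD: row C14, SD | same, SD |
| 3, look-back | skips NE only; finds SD at day 112 | skips NE and SD; finds PR at day 56 |
| 3, pair | SD/CR is not listed; fallback row C24, SD | PR/PR, PR |
| Carry forward | best of (SD, SD) = **SD** | best of (PR, SD) = **PR** |

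**Timing.** First scan on day 42, 48, 49, 56 or 63, crossed with gaps of 28, 35 or 56 days, gives 5 × 3 = 15 combinations. All 15 return SD for PR, SD, CR and PR for PR, SD, PR. If the SD scan falls less than 28 days before the CR (days 56, 84, 105), the look-back passes over it and PR, SD, CR returns PR. Scheduled scans are never that close.

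**How many patterns.** Among all three- and four-visit sequences with no PD and no earlier CR, replacing a last PR by CR worsens BOR in one three-visit pattern (PR, SD, x) and five four-visit patterns: PR, SD, SD, x; PR, SD, NE, x; PR, NE, SD, x; SD, PR, SD, x; and NE, PR, SD, x.

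**What happens afterwards.**

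- PR, SD, CR, CR gives CR, so a later confirming CR repairs it.
- PR, SD, CR, PD stays SD.
- PR, SD, CR followed by PR or SD goes to a data query. The carried-forward value is SD unless the query is resolved as the Table 14-3 footnote describes for an over-called CR or a non-evaluable non-target assessment, where the best response is PR.
- A PR already confirmed before the SD is kept by step iii.

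**Size.** One subject in 40 is 1/40 = 2.5 percentage points. At the protocol's planning rate, 8/40 = 20.0% has a Clopper-Pearson 95% interval of 9.1% to 35.6%, matching the stated 9% to 36%. With one responder lost, 7/40 = 17.5% (7.3% to 32.8%).

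**The case against.** The strongest reply comes from the protocol. It asks for a consecutive confirming scan and maps PR followed by SD to SD. On that rule SD is the conforming result for PR, SD, CR, and the undisclosed departure is the branch that skips SD when the current scan is PR. This stands, and it decides which branch should change. A reader might infer that PR, SD, CR subjects are true responders whom the plan wrongly discards, so that ORR is understated. The documents do not support that: such a subject is a responder under the SAP text but not under the protocol's rule. What the reply does not do is remove the inconsistency, since no reading of either document explains accepting PR, SD, PR while rejecting PR, SD, CR.

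A second reply is that Table 14-4 only outlines steps, the prose rules are stated to apply, and SAP Appendix C contains no code for BOR. That also stands as far as it goes. The finding is a conflict between two parts of the specification, and it shows no misclassified subject.

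A third is that the reach is narrow. DCR is unchanged because SD counts as disease control. At an interim, step 2 already counts a CR with its next scan pending. No hypothesis is tested, and the NoGo criterion serves interim futility only. A reader might infer that the futility rule is generally distorted; the documents do not support this either. An interim count could be touched only through subjects who have stopped assessments, for whom the interim value equals the confirmed one.

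**Conclusion.** SAP Appendix D is internally inconsistent and needs correcting, at low priority. With scans at least 28 days apart and no later confirming CR, Table 14-4 gives SD for PR, SD, CR against the appendix's own text, and PR for PR, SD, PR. Each case moves ORR by 2.5 points if n = 40, and by more if the RECIST-evaluable set is smaller, and it removes the subject from DOR.

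The assumptions are as follows. The fallback is read literally, with the immediately preceding scan as the first time point in Table 14-3. The pattern is taken to be rare, because it needs a PR, a return to SD and then a CR; the documents give no frequency, so only the effect per case can be stated. The SAP was written against protocol amendment 6, whereas the protocol at hand is amendment 7. The amendment 7 summary names only the non-target lesion table as changed in Appendix 8, so the confirmation rule is assumed to be the same in both.

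**What to change.** Decide which confirmation rule governs, then treat both branches of step 1 ii(a) alike.

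- **If the SAP text stands:** when the current visit is CR, first look for a CR at least 28 days earlier, skipping NE only, and assign CR if found. If that fails, look for a PR at least 28 days earlier, skipping NE and SD, and assign PR if found. State the 28-day condition in both steps; without it, an unscheduled CR soon after a PR would count as confirmation. Run on the sequences above, this gives PR for PR, SD, CR, keeps CR, SD, CR at SD, leaves both worked examples unchanged, and removes every reversal found. Add to SAP Section 10 that SD gaps depart from the protocol's consecutive-confirmation rule.
- **If the protocol rule governs:** remove the SD skip from the PR branch, and remove SD from the Appendix D text and its worked example. Both sequences then give SD.

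Either way, add PR, SD, CR as a worked example so that the text and the program can be checked against each other. The cost is a line or two of SAP text and one program branch, plus a Section 10 entry under the first option. No new data are needed.
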